4.4. Trial Design

A single-centre single-arm phase II, Simon's two-stage optimum design study to assess the efficacy of blinatumomab in patients with molecular relapse or molecular persistence of acute myeloid leukaemia (AML) with a t(8;21). Given that the current standard of care is FLAG-Ida, blinatumomab will be considered worth pursuing if it achieves a 75% molecular remission rate; a rate less than 50% would be considered unpromising. Using the recommended design characteristics of 85% power and 15% significance level, 7 evaluable patients will be recruited in stage I. There will need to be at least 4 responses to proceed to stage II, where a further 10 patients will be recruited. Otherwise, the trial will not proceed. If the study proceeds to stage II, and 17 evaluable patients have been recruited, the success criteria are that there are at least 11 responses in total. (Figure 1)

All enrolled patients will be evaluated at each stage for the primary endpoint of molecular complete response after one cycle of treatment, as well as safety and tolerability

[figure not shown]

Figure 1 – flowchart of planned patients' recruitment and stopping rules for the study

An Academic Health Sciences Centre for London

Pioneering better health for all

4.5. Schedule of events

	Screening (within 21							Cycl	es 1 to	4					90 days	2-Year Follow-	NACAL -I
	days prior to treatment)	Day 1*§	Day 2§	Day 3	Day 4	Day 8 (+/- 2d)	Day 11	Day 15 (+/- 2d)	Day 18	Day 22 (+/- 2d)	Day 25	Day 29 (+/- 2d)	Days 30-42 (+ 7d)	Unschedule d visit	after last treatment (+/- 5d)	up Period ^	Withdrawal visit
Informed consent	X																
Eligibility assessment	Х																
Medical history	Х																
Physical exam,vital signs and temperature	х	х	х	Х		Х		Х		Х		Х		Х	Х	Х	х
Neurological exam and writing test	Х	Х	Х	Х		Х		Х		Х		Х		Х	Х		Х
ECOG performance status	Х															Х	
ECG	Х														Х		Х
Urinalysis	Х	Х	Х	Х		Х		Х		Х		Х			Х	Х	Х
Pregnancy test (if applicable)	Х														Х		Х
Haematology and biochemistry	Х	Х	Х	Х		Х		Х		Х		Х		Х	Х	Х	Х
Virology (HIV, HBV, HCV)	Х																
Serum immunoglobulins	Х											Х			Х		Х

	' after last													2-Year Follow-	With drawal		
	days prior to treatment)	Day 1*§	Day 2§	Day 3	Day 4	Day 8 (+/- 2d)	Day 11	Day 15 (+/- 2d)	Day 18	Day 22 (+/- 2d)	Day 25	Day 29 (+/- 2d)	Days 30-42 (+ 7d)	Unschedule d visit	treatment (+/- 5d)	up Period	Withdrawal visit
Bone Marrow aspirate (+/- trephine)	Х											X ⁺				Х	
Response assessment												Х					
Blinatumomab infusion			Continuous infusion days 1 – 28 of each cycle Treatment break														
CADD pump attendance#		х			х	х	х	х	х	х	х	х					
Concomitant medications	Х		<< Ongoing assessment >>														
Adverse events			<< Ongoing assessment until 90 days after treatment discontinuation >>								X						
Supportive Care Requirements						<<	Ongoi	ng assessi	ment ur	ntil treatme	nt disco	ontinuation	>>				Х

NOTES:

Data on concomitant medications, adverse events and supportive care requirements may be collected during unscheduled visits

[figure not shown]
§ indicates inpatient visits. All other scheduled visits are outpatient visits.

*Clinical assessments and laboratory assessment performed within 3 days prior to the first dose of blinatumomab will not have to be repeated on day 1 cycle 1

^For patients who did not undergo allogeneic HSCT, Efficacy follow-up visits for assessment of molecular relapse and until haematological relapse will take place 3-monthly (calculated from cycle 1 day 1) within the first year and 6-monthly within the second year until completion of a 2-year period after treatment with blinatumomab. Telephone follow-up will be performed for patients who have undergone HSCT.

*Includes initial connection, twice weekly change of infusion bag, and disconnection. To account for weekends and bank holidays, each cycle should start on a Tuesday. Infusion bag changes will therefore occur on Tuesdays and Fridays

[†]In case of technically suboptimal samples, a repeat bone marrow aspiration may need to be performed

An Academic Health Sciences Centre for London

Pioneering better health for all

5. Trial Medication

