5.6. Administration

Blinatumomab will be administered as a continuous intravenous (CIV) infusion at a constant flow rate rate as specified on the prescription, via a low protein binding infusion line with 0.2 micron inline filter using a CADD Ambulatory Infusion Pump. The infusion is for four weeks followed by a two-week infusion free interval, which may be prolonged for up to seven more days, if deemed necessary. There should be no planned interruptions in the infusion, e.g. for i.v. administration of other medication. Patients will be hospitalized during at least the first three days after start of infusion of the first treatment cycle and during at least the first two days after start of infusion of subsequent cycles. After interruption of treatment for more than 4 hours, the infusion should be restarted in the hospital, under supervision of the investigator. After interruptions for up to 4 hours, the infusion can be continued without specific measures.

The CADD infusion bags will be prepared as either 72 hour or 96 hour infusions, with the bags being changed twice a week. To account for weekends and bank holidays, this will occur on Tuesdays and Fridays. Each cycle should being on a Tuesday.

The infusion rate of the 250mL bag depends on the duration of the infusion:

- 72 hour infusions: Administer at a constant infusion rate of 3.33 mL/h over 72 hours, to achieve a final infusion volume of 240 mL for each subject. Any remaining infusion solution volume present in the infusion lines must be discarded.
- 96 hour infusions: Administer at a constant infusion rate of 2.5 mL/h over 96 hours, to achieve a final infusion volume of 240 mL for each subject. Any remaining infusion solution volume present in the infusion lines must be discarded.

Problems with the infusion bag, pump, or intravenous access should be rectified as soon as possible by contacting the Acute Oncology Service on [name]

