5.10. Patient Monitoring

The patient is to be an in-patient during the first two days of each treatment cycle (three days of the first cycle) because of potential side effects associated with T cell redistribution and potential cytokine release effects triggered by the administration of blinatumomab. Nurses and physicians trained in management of medical emergencies should be available for immediate intervention in case of complications.

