5.11. Out-patient Treatment

Blinatumomab will be administered on an in-patient basis during at least the first three days after start of infusion of the first treatment cycle and during at least the first two days after start of infusion of each following cycle or if necessary for restart of treatment following temporary discontinuations due to adverse events. Afterwards the treatment will be continued on an out-patient basis, if it seems to be safe and feasible to the investigator. For the approval of an out-patient treatment the following conditions will have to be met:

- The patient will be able and willing to visit the investigator at the study centre
 according to the study visit schedule, which is weekly during the infusion period
 assuring infusion bag change, monitoring of vital signs, and
 monitoring/documentation of AE/SAE.
- In addition, regular visits to the study site infusion centre by the patient for review by a well-trained nurse or medical doctor being thoroughly familiar with the study will be guaranteed assuring infusion bag change, maintenance of port, and, monitoring of vital signs.
- A continuous ambulatory drug delivery (CADD) pump will monitor delivery of the IMP.

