7.2. Treatment Period (Cycle 1 - 4)

Patients will be hospitalised during at least the first three days of the first cycle and during at least the first two days of each following cycle. Before starting the infusion of blinatumomab, the patient will be examined physically and blood samples for safety laboratory parameters will be taken. For starting the study treatment the laboratory results will not have to be awaited.

Following the start of the infusion AE/SAE and concomitant medication will be evaluated continuously throughout the whole study until the 90-day visit. After the 90-day visit, only (S)AEs potentially related to blinatumomab should be documented in the CRF (and reported to the sponsor, if applicable). In addition, only anti-leukemic concomitant medication and medication related to blinatumomab related (serious) adverse events should be documented in the CRF. The vital signs and the laboratory tests will be repeated on D2 and D3 and at each visit during the treatment period.

Replacement of infusion bags will be performed as described in the Operations Manual. CADD pump infusion bags will be changed twice a week. To account for weekends and bank holidays, this will be on Tuesdays and Fridays. Each treatment cycle should begin on a Tuesday.

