7.2.1. Treatment Period (Day 1 - Day 29 of each treatment cycle)

Prior to Infusion (D1)

- Physical examination
- Vital signs/temperature it is recommended to monitor the patient's vital signs continuously every four hours during the first 24 hours after start of treatment/dose step.
- Neurological examination and writing test
- Routine bloods, U/E, LFTs, LDH, Coagulations screen, FBC (aproximately 30mL of blood)
- Urinalysis
- Concomitant medication
- AE/SAE assessment
- CADD pump attachment

During Infusion (D2 to D22)

The following procedures and tests will be performed on D1 to D29 during blinatumomab infusion:

- Physical examination (D2, D3, D8, D15, D22)
- Vital signs/temperature (D2, D3, D8, D15, D22). On D2 and D3 vital signs should be measured at least twice a day
- Neurological examination and writing test (D2, D3, D8, D15, D22)
- Routine bloods, U/E, LFTs, LDH, Coagulations screen, FBC (D2, D3, D8, D15, D22) (aproximately 30mL of blood)
- Concomitant medication ()
- AE/SAE assessment ()
- CADD pump change on days 4, 8, 11, 15, 22 and 25

At the end of the infusion period of cycle two to four the procedures and tests of D29 of the first cycle will be repeated.

End of Infusion (D29)

The following procedures and tests will be performed on D29 (end of infusion):

- Physical examination
- Vital signs/temperature
- Neurological examination and writing test
- Bone marrow aspiration/biopsy
- Routine bloods, U/E, LFTs, LDH, Coagulations screen, FBC (aproximately 30mL of blood)
- Serum Immunoglobulins (IgG)
- Concomitant medication
- AE/SAE assessment

Infusion free Interval from Day 30 to Day 43 (applies to each treatment cycle)

After completion of the 4-week infusion period a 2-week infusion-free period will follow before a new cycle starts. During this time, the patient will not need to visit the study centre. The infusion free interval may be prolonged for up to seven more days, if deemed necessary. If the treatment will be continued, study day 43 of the previous cycle will be day 1 of the subsequent cycle.

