7.2.2. D43/D1 of Subsequent Cycle

If the treatment will be continued with a further cycle, the patient will be hospitalised for two days and the following procedures and tests will be performed:

- Physical examination
- ECOG performance status
- Neurological examination and writing test
- Vital signs/temperature
- Routine bloods, U/E, LFTs, LDH, Coagulations screen, FBC (aproximately 30mL of blood)
- Urinalysis
- Concomitant medication
- AE/SAE assessment
- Confirmatory bone marrow aspiration in case of central MRD result shows that the previous sample was technically inadequate.

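### The schedule of events makes cycle 1 day 3 an outpatient visit, although four sections of the text require three days in hospital in cycle 1

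*Protocol*

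**What the plan says.** **Schedule.** Protocol section 4.5 shows the treatment visits in one block of columns covering cycles 1 to 4. The § symbol stands on day 1 and day 2 and not on day 3. The legend states that § "indicates inpatient visits. All other scheduled visits are outpatient visits".

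**Text on cycle 1.** Four sections deal with the hospital stay:

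- Section 5.6: "Patients will be hospitalized during at least the first three days after start of infusion of the first treatment cycle".
- Section 5.10: "The patient is to be an in-patient during the first two days of each treatment cycle (three days of the first cycle").
- Section 5.11: treatment is "administered on an in-patient basis during at least the first three days after start of infusion of the first treatment cycle".
- Section 7.2: "Patients will be hospitalised during at least the first three days of the first cycle".

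**Text on later cycles.** Section 5.6 asks for hospital care "during at least the first two days after start of infusion of subsequent cycles". Sections 5.10, 5.11 and 7.2 also give two days, and section 7.2.2 says that at the start of a further cycle "the patient will be hospitalised for two days".

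**The concern.** The legend does more than leave day 3 unmarked. It assigns every unmarked scheduled visit to outpatient care, and day 3 is a scheduled visit with physical, neurological and laboratory assessments. The schedule therefore gives a rule for cycle 1 day 3 that is the opposite of the rule in the text.

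Section 5.10 explains that the inpatient days exist because of T-cell redistribution and possible cytokine release, and it wants trained staff at hand to intervene. Visits are commonly booked from the schedule table. Staff who did so could send a cycle 1 patient home a day early, which would deviate from four sections of the same protocol. Section 6.8 allows up to two further sites in stage II, whose staff would be new to the study.

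There is a smaller link to the analysis. Days of hospital admission at 1, 3 and 6 months is a secondary endpoint (section 4.3). The admission that the protocol itself requires is part of that count, so the required minimum should be unambiguous.

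**Working it through.** The protocol states no figure that needs reproducing here. The check is a comparison of the two sets of rules, followed by a count.

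**Step 1: does the schedule cover cycle 1?** Yes. The columns are headed for cycles 1 to 4, and one footnote refers specifically to day 1 of cycle 1.

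**Step 2: required inpatient days, counted as days of the cycle.**

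| Cycle | Schedule (4.5) | Text (5.6, 5.10, 5.11, 7.2) | Difference |
|---|---|---|---|
| 1 | 2 (days 1 and 2) | 3 or more | 3 − 2 = 1 |
| 2, 3, 4 (each) | 2 | 2 (a minimum in 5.6, 5.11 and 7.2) | 2 − 2 = 0 |
| All four | 4 × 2 = 8 | 3 + 2 + 2 + 2 = 9 | 1 |

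**Step 3: does the result depend on how days are counted?** Sections 5.10 and 7.2 count days of the cycle, while 5.6 and 5.11 count from the start of infusion. If three days means days 1 to 3, day 3 is an inpatient day. If it means a full 72 hours from the start of infusion, day 3 still lies inside the stay. The cycle 1 conflict exists on both readings. The agreement in cycles 2 to 4 is less firm: 48 elapsed hours would run into day 3 there. Sections 5.10, 7.2 and 7.2.2 point to the day-of-cycle count, which is the one used in the table.

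**Step 4: does anything reconcile the two?** In sections 5.6, 5.11 and 7.2 the three days are a minimum, and the schedule falls below it. Section 5.11 allows outpatient treatment only after the inpatient days. No schedule footnote makes an exception for cycle 1 day 3, and the protocol does not say whether table or text prevails.

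**Step 5: how many patients?** The planned total is 7 + 10 = 17 (section 10.1), each with one cycle 1 day 3 visit. It is 7 if the trial stops after stage I. These are counts of evaluable patients, and section 6.6 replaces those who withdraw, so the number treated could be higher.

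**Step 6: effect on the hospital-days endpoint.** A cycle lasts six weeks, so no later cycle can start within the one-month count. The stay required in cycle 1 is 2 days by the schedule and 3 by the text. If a patient were managed by the schedule, the count could be about one day lower.

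**The case against.** The strongest reply is that the intention is not in doubt. Four sections state the three-day rule consistently, and the table has compressed four cycles into one set of columns that suits cycles 2 to 4. Section 5.11 also makes outpatient care depend on the investigator judging it safe and feasible and on listed conditions, so a booking made from the table does not by itself discharge anyone. Stage I runs at a single site.

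Much of this is fair. It lowers the chance of harm, and a careful reader would follow the text. It does not remove the conflict: the condition in section 5.11 takes effect only after the three days, so it restates the rule that the schedule breaks.

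A second reply concerns vital signs. Section 7.2.1 says "On D2 and D3 vital signs should be measured at least twice a day", which would be awkward in a single clinic visit and might seem to support an inpatient day 3. That section covers every cycle, however, including those in which the text allows discharge after two days. The instruction therefore cannot decide the cycle 1 question, and the conclusion does not rest on it.

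Third, the day 3 assessments take place under either reading and nothing in the primary inference changes. Both statements are correct, and they limit the weight of the point.

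**Conclusion.** The point holds. The schedule and the text give incompatible rules for cycle 1 day 3, and the text is clearly the intended one. The size is one inpatient day in each treated patient's first cycle: 17 patients if both stages fill as planned, 7 if only stage I runs, before any replacements. On a day-of-cycle count, cycles 2 to 4 agree.

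The matter should be corrected because the day in question is kept in hospital for safety and the schedule is a working document. It does not affect the response criterion, the two-stage boundaries, or the type I and type II error rates. The possible shift of about one day in the hospital-days endpoint arises only if patients are actually managed by the schedule rather than the text.

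The conclusion assumes that the inpatient symbol is absent from day 3 in the printed table, as it is in both copies of the table header in the text version. One figure next to the legend is not reproduced there.

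**What to change.** Add a footnote to the day 3 column in section 4.5 stating that day 3 is an inpatient day in cycle 1, with a minimum of three inpatient days in cycle 1 and two in each later cycle. Amend the legend sentence so that the outpatient default excludes cycle 1 day 3. Sections 5.6, 5.10, 5.11 and 7.2 can stay as they are for this purpose.

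The cost is one footnote and one edited sentence in the next protocol version. No assessment, sample size or analysis changes.

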5.1. Investigational Medicinal Product

Blinatumomab (AMG103) is a murine recombinant single-chain antibody derivative that combines in one molecule the binding specificity for both the pan-B cell antigen CD19 and the epsilon chain of the T cell receptor/CD3 complex. The molecular weight of blinatumomab is approximately 54 kDa. Blinatumomab belongs to a new series of compounds called bispecific T-cell engagers (BiTE). The antibody is produced by mammalian (Chinese hamster ovarian, CHO) cell suspension culture and purified by affinity and ion exchange chromatography, including viral inactivation and removal procedures.

Blinatumomab is manufactured and will be supplied by Amgen. Information regarding the ordering process, accountability, compliance, returns and destruction will be outlined in the Trial Pharmacy Manual. Delivery lead time is 5 days. Temperature excursions are to be reported to [contact] as per the parameters outlined in the Pharmacy Manual.

5.2. Formulation, packaging and labelling

The blinatumomab formulation will be supplied as single-use injection vials containing a white to off-white, lyophilized powder intended for intravenous administration following reconstitution with sterile water for injection (sWFI). Each vial contains a target of 38.5 µg of Blinatumomab and there are 36 vials in a kit.

The formulation will be filled in 4 mL borosilicate clear vials containing the following excipients: citric acid monohydrate, trehalose dihydrate, lysine hydrochloride and polysorbate 80.

The stabiliser solution will be supplied as a 10 mL vial of a clear, colourless-to-slightly-yellow liquid concentrate composed with citrate. The product specific diluent consists of 25 mM citric acid monohydrate, 1.25 M L-lysine hydrochloride and 0.1% (w/v) polysorbate-80 at pH 7. The information presented on the labels for the IMP will be annex 13 compliant and comply with applicable national and local regulations.

5.3. Storage of IMP

The blinatumomab formulation and the stabiliser solution should both be stored between 2°C and 8°C in their original outer package within a secure environment, protected from light and separated from other medication or investigational products. Do not freeze. Blinatumomab concentrate does not contain any preservatives. The reconstitution has to be done in controlled and validated aseptic conditions. Parenteral products should be inspected visually for particulate matters and discoloration beyond a pale yellow colour (due to the administration of the stabiliser solution) prior to administration. If these are present, blinatumomab final solution must not be used and the Sponsor should be informed immediately. Please refer to the Investigator's Brochure for further details, particularly for current data concerning the stability of blinatumomab. If shelf-life of the product will be extended during the trial supported by corresponding stability data, relabelling of study medication at the pharmacies is possible, but must follow detailed instructions provided in the Pharmacy File.

5.4. Preparation

The final blinatumomab solution for infusion should be prepared in a clean, sterile environment using aseptic techniques at the study site's pharmacy, even if the patient is treated as an outpatient. The volume (dose) of blinatumomab is calculated based on the patient's weight. As all patients will be greater than 45kg,the dose is 28 mcg/day.

Blinatumomab lyophilized powder for solution, the stabiliser solution and the final solution for infusion are for single use only. Any remaining concentrate or final solution for infusion should be disposed of.

First, the lyophilized formulation of blinatumomab will be reconstituted with 3 mL sterile water for injection (sWFI). Then, it will be further diluted into a 0.9% sodium chloride solution (normal saline) intended for intravenous infusion in 250 mL infusion bags. The used water for injection and sodium chloride solution must be commercially available and marketed in the United Kingdom for the purpose of intravenous infusion, marked with the exact Pharmacopeia term. Since blinatumomab will be administered via continuous intravenous route, it needs to be stabilized at low concentrations and must be prevented from adsorbing to surfaces. Therefore, the normal saline bag must be conditioned by prior addition of a product-specific diluent (stabiliser solution), resulting in a final diluent concentration of 0.5 mM citrate, 25 mM lysine hydrochloride and 0.002% (w/v) polysorbate80. Detailed instructions regarding the reconstitution and dilution of blinatumomab as well as the preparation of the IV bag prior to administration will be provided to the respective pharmacy before the investigational product will be applied for the first time (refer to Pharmacy Manual).

Blinatumomab will be administered via a continuous ambulatory drug delivery (CADD) pump. Blinatumomab solution for infusion must be administered at ambient temperature and must not be kept at ambient temperature more than 96 hours.

For storage prior to administration, the prepared infusion solution must be kept at 2°C to 8°C. The total storage and administration time must not exceed 10 days

